The protocol as described includes the entire subject set, which allow for comparisons between obese girls with and without PCOS. OGTT with tracers will be conducted in all subjects, and overnight assessment of HDNL in 20 subjects (10 with PCOS and 10 without). However, data from the first 6-12 subjects (both PCOS and non-PCOS) will be immediately evaluated to see if any changes are needed in terms of protocol details. The specific points that are to be evaluated are listed below:

1) OGTT with glucose and glycerol tracers

- a. Purpose: Develop an oral stimulus model to assess hepatic and adipose insulin sensitivity.
- i. Question 1. Is 4 hours post oral load long enough to model hepatic and adipose insulin sensitivity?
 1. Rationale: Our preliminary data from OGTT's in obese girls indicates that subjects' insulin and glucose concentrations have not returned to baseline by 2 hours. Data from adults showed that all non-diabetic adults were back to baseline by 3.5 hours.
 2. Measurement. Serum glucose and insulin will be measured post-glucose load for 4 hours in the first 6 subjects. If 4 hours post glucose values are within 10 mg/dL for glucose and 10 IU/mL for insulin relative to baseline values, 4 hours will be considered sufficient.
- ii. We are revising the protocol to 6 hours based on our results from our first several subjects. Question 2: Are glucose and glycerol Ra during the OGTT similar to those obtained with a hyper-insulinemic euglycemic clamp.
 1. Rational: Peak insulin concentrations are similar between an OGTT and a clamp, thus Ra rates should also be similar. Comparisons in adults of the glucose Ra from clamps and an oral meal challenge were similar.
 2. Measurement: The peak suppressed glucose and glycerol Ra for the first 12 subjects will be compared to peak suppressed Ra values calculated from data from 70 girls during hyper-insulinemic euglycemic clamps.
 3. Revision plan if model not correct: None. Findings of either similar or different glucose and glycerol Ra are valuable information.

2) Measurement of Hepatic De Novo Lipogenesis (HDNL)

- a. Purpose: Optimize a model to asses HDNL with minimal blood draws, minimal time of tracer intervention and no interference with measures of glucose and glycerol
 - Ra

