If a subject experiences any of the following, the subject will be withdrawn from the study.

1. Inability to complete study procedures
2. Abnormal screening labs (LFT's >4 times elevate, HbA1C>6.4%, Hg <9 mg/dL)
3. Subject becomes pregnant during study

D. Protocol Stopping Criteria

If one or more subjects experience any of the SAE's listed above, the PI will consult with the mentor prior to continuing study visits with subjects. The mentor and RSA will consult about the significance of the SAE's and make a recommendation to the PI.

VII. Data Analysis Plan:

Statistical Plan for Method Development: The previously described tracer protocol and mathematical modeling with any refinements will be performed in an additional 9 subjects. Outcome measures (raw suppressed glucose and glycerol Ra, insulin concentration required for 50 percent of peak suppression and percent suppression of basal Ra) will be compared between the OG subjects and a matched cohort of girls who have undergone hyperinsulinemic euglycemic clamps with identical glucose and glycerol tracer infusion rates. Subjects in the two groups will be matched on PCOS diagnosis, race, percent body fat, percent liver fat, and time post-menarche. An equivalence design will be used to compare the outcomes in the two groups and to demonstrate whether there are clinically significant differences in outcomes from the OG model and the hyperinsulinemic clamp. For purposes of sample size calculation, we used estimates from the investigator's pilot study. Using an equivalence limit of one standard deviation for each outcome measure (SD=50 units for glycerol IC50 and SD=39 units for glucose IC50) and a correlation of 0.2 between outcomes on matched subjects, 15 matched pairs gives 80% power to demonstrate equivalence. 70 girls have completed the hyperinsulinemic euglycemic clamps, so adequate matching will be possible.

Overall Project Statistical Plan:

Power calculation: The primary outcome is hepatic IR measured as IC₅₀ glucose Ra. Using our preliminary data, a two-tailed t-test and an alpha of 0.05, completing 13 controls and 32 PCOS provides 86% power to detect a difference of 35 IU/L in the insulin concentration.

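### The oral glucose versus clamp equivalence test leaves about 55 of the 70 existing clamp girls unused; an adjusted analysis on all comparable girls would raise power cheaply

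*Combined protocol and SAP*

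**What the plan says.** The Statistical Plan for Method Development (section VII) compares suppressed glucose and glycerol Ra, the insulin concentration for half-maximal suppression and percent suppression between OG girls and girls who have already had a clamp. On the pairing it says: "Subjects in the two groups will be matched on PCOS diagnosis, race, percent body fat, percent liver fat, and time post-menarche". The margin is set by "Using an equivalence limit of one standard deviation for each outcome measure (SD=50 units for glycerol IC50 and SD=39 units for glucose IC50". The sizing also takes 0.2 as the within-pair correlation. The outcome of the calculation, with the clamp girls named only as a pool for finding partners, is: "15 matched pairs gives 80% power to demonstrate equivalence. 70 girls have completed the hyperinsulinemic euglycemic clamps, so adequate matching will be possible". No one-to-many matching, covariate adjustment or other use of the unpaired clamp girls is planned for this test.

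The number of OG girls is not settled. The same paragraph says that the tracer protocol and modelling "will be performed in an additional 9 subjects", yet it powers 15 pairs. Aim 1 reaches 15 as an initial 6 plus a further 9. It does not say whether the initial 6 enter the equivalence test.

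Section IV (Limitation of Method Development, Question 2) plans a second comparison, in which peak suppressed Ra in the first 12 OG girls is "compared to peak suppressed Ra values calculated from data from 70 girls during hyper-insulinemic euglycemic clamps". It gives no adjustment, margin or power.

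**The concern.** The clamp data already exist, so the scarce resource is OG girls. Pairing each OG girl with one clamp girl gives the clamp mean the same sampling error as the OG mean, although the pool could make it much smaller. Neither planned analysis both uses all 70 girls and adjusts for the five matching variables: the equivalence test adjusts by pairing but uses few clamp girls, and the section IV comparison uses all 70 but adjusts for nothing.

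At stake is the chance that a sound method ends with an inconclusive equivalence result when existing data could have settled the question. Aim 1B says that the new method's Ra values need to be shown to lie within the range of the clamp's.

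**Working it through.** **Inputs from section VII.** Margin 1 SD (50 for glycerol IC50, 39 for glucose IC50, so 1.0 in SD units for both), pair correlation 0.2, 15 pairs, 70 clamp girls. Unused in this test: 70 − 15 = 55.

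**Assumptions.** Alpha is not stated; I take two one-sided tests at 0.05 (a 90% CI inside the margin) and a true difference of 0. If pairs match exactly on the five variables, a pair correlation of 0.2 corresponds to those variables explaining 20% of the variance, which leaves a residual variance of 0.8. The model is given 5 covariate degrees of freedom; race could need more.

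**Step 1: the plan's figure.** SE = √(2(1 − 0.2)/15) = 0.327, on 14 df. Exact power is 79.4%, which reproduces the stated 80%. At 0.025 per side it would be 62.6%, so 0.05 is the natural reading.

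**Step 2: all 70 clamp girls, equal variances.** SE = √(0.8(1/15 + 1/70)) = 0.254, on 15 + 70 − 7 = 78 df. Power is 97.6%, or 96.8% by simulation with chance imbalance in five covariates.

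**Step 3: less favourable cases, 15 OG girls** (compare 79.4% for pairs).

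| Case | Power |
|---|---|
| Covariates explain nothing, SE = √(1/15 + 1/70) = 0.285 | 93.4% |
| Only 57 clamp girls usable | 97.0% |
| Only 30 clamp girls usable | 93.2% |
| Covariate imbalance inflates the variance 1.5-fold, SE = √(1.5 × 0.8(1/15 + 1/70)) = 0.312 | 87.5% |
| One-to-four matching, 15 sets | 95.8% |

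With a true difference of 0.25 SD, power is 68% for pairs and 90% for 15 v 70.

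**Step 4: unequal variances.** Let k be the OG SD divided by the clamp SD, with the margin read as 1 clamp SD. Pairs: SE = √((1 + k² − 0.4k)/15). Model with a Welch-type SE: √(0.8(k²/15 + 1/70)) with Satterthwaite df.

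| k | Pairs: SE, power | Model: SE, power |
|---|---|---|
| 1 | 0.327, 79% | 0.254, 97% |
| 1.25 | 0.371, 64% | 0.308, 86% |
| 1.5 | 0.420, about 46% | 0.363, 68% |

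A pooled-variance model is not safe here. With 15 v 70, its false-equivalence rate at the margin rises from 5% to about 8% at k = 1.25 and about 10% at k = 1.5. The Welch-type version and the paired test stay near 5%.

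**Step 5: only 9 OG girls.** Pairs: SE = √(1.6/9) = 0.422, power 42%. Against 70 clamp girls at equal variances: SE = √(0.8(1/9 + 1/70)) = 0.317. Power is 86% pooled by formula, 83% by simulation with chance imbalance, and 80% with a Welch-type SE. The Welch-type figure falls to 55% at k = 1.25 and 32% at k = 1.5.

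**The case against.** The strongest reply is that nothing here is wrong. The plan names its matching variables, margin, correlation and power, and the power is right. Pairing on named confounders is an accepted design and does not lean on a linear model. That stands: this is a gain in efficiency, not the correction of an error.

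The reply also has force on validity. OG and clamp outcomes come from different methods, and nothing in the documents shows equal variances. With a small OG group and a large clamp group, a pooled standard error would declare equivalence too often if OG outcomes are the more variable. This stands too, and is why the fix specifies an unequal-variance standard error.

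Comparability is a further limit. The make-up of the 70 is not given. Table 1 lists 19 control, 38 PCOS and 40 T2D girls, 97 in all, so its 57 non-diabetic girls cannot be assumed to be among the 70. Section VIII says the previous protocol excluded girls over 250 lbs; this one excludes above 300 lbs. Systematic imbalance is therefore plausible, and the 97% is a best case.

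Two stronger readings should be resisted. A reader might infer that the trial's primary outcome depends on this test. It does not: the primary analysis compares PCOS with control girls, both measured by the same OGTT tracer method, and section IV plans no revision whether the OG and clamp Ra values agree or differ. A reader might also infer that the pairs would be poorly matched. The documents give neither a matching tolerance nor the clamp girls' distribution on the five variables, so this cannot be shown either way.

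**Conclusion.** The point holds as a cheap improvement. With 15 OG girls, using all comparable clamp girls with adjustment raises power from 79% to about 97% at equal variances, and to about 88–93% if the covariates explain nothing or imbalance inflates the variance 1.5-fold. If OG outcomes are more variable, the gain is from 64% to 86% (SD ratio 1.25) or from about 46% to 68% (ratio 1.5). The model beats one-to-one pairs at every ratio checked.

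These figures assume two one-sided tests at 0.05, a true difference of 0 unless stated, covariates explaining 20% of the variance unless stated, and clamp girls comparable after adjustment.

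It would be tempting to call 42% the planned power. That holds only if the initial 6 OG girls are left out, and Aim 1's count of 15 points the other way. In that case the model gives about 80–86% at equal variances. Nor are the unpaired clamp girls ignored altogether, since the section IV comparison uses all 70; they are unused in the equivalence test only.

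**What to change.** - Make the main OG–clamp equivalence analysis a model on all OG girls and all comparable (non-diabetic) clamp girls, with terms for method, PCOS status, race, percent body fat, percent liver fat and time post-menarche. One-to-many matching on the same variables is an alternative.
- Use a Welch-type or small-sample heteroscedasticity-robust standard error, and judge equivalence from the 90% CI of the method term.
- Keep the one-to-one pairs as a sensitivity analysis.
- Use the same adjusted model for the section IV comparison with the 70 girls.
- State the alpha, whether 9 or 15 OG girls enter, and the make-up of the 70 clamp girls. Restate power as a range over variance ratio and covariate imbalance.

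The cost is analysis wording: no added recruitment, visits or measurements. The downside is reliance on the covariate model and on the clamp girls' comparability. The paired analysis gives a partial check on the first; describing the clamp cohort addresses the second.

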Description: Body composition will be measured using the DEXA technique on the pediatric CTRC and will be used to derive fat-free mass and % body fat. This technique relies on the absorption of dual electron wavelengths for the assessment of body fat, lean tissue, and bone mineral density. During the procedure, the subject will be supine on the measurement table, and the arm of the machine will slowly pass over their body.

Risk: Minimal. Radiation exposure

Justification/Minimization: Body composition is best assed via DEXA, and the amount of muscle mass is needed to standardize the OGTT results, since body weight can vary greatly. This procedure will deliver the radiation exposure that is 2 times the level of background radiation in Colorado.

Subjects will be tested for pregnancy immediately prior to DEXA, to ensure that they are not pregnant.

9. Endopat and Dynapulse

Description: The Dynapulse Pathway and the EndoPat system are noninvasive portable systems that measure brachial artery distensibility and endothelial function, utilizing a standard sphygmomanometer cuff inflated in the same fashion as a sphygmomanometer to obtain blood pressure. The instrument derives brachial artery distensibility using the technique of pulse waveform analysis of arterial pressure signals obtained from the sphygmomanometer.

Risk: This procedure may lead to mild discomfort due to the blood pressure cuff being inflated.

Justification/Minimization: Endothelial function is an novel measure in PCOS and will aid in the determination of cardiovascular dysfunction with this population. A trained cardiovascular technician will be on hand to witness the procedure.

10. Body fat distribution

Description: Height, weight, waist circumference, and hip circumference will be measured. Body fat distribution will be determined using the waist-to-hip ratio where the waist circumference is measured 1/2 the distance from the xiphoid process to the navel and the hip circumference is measured at the level of the greater trochanter.

Risk: None

Justification/Minimization: IR has been associated with central obesity, as has hyperandrogenism. Whereas we are measuring central obesity with MRI, it is important to see if this simple non-invasive measure matches the MRI results, as it is a much simpler measure to follow clinically.

11: Accelerometer:

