Differences between the two primary groups (PCOS, controls) will be assessed with a t test or for non-normally distributed data a non-parametric test such as Mann-Whitney U. Secondary outcomes include a Pearson correlation test of potentially related variables followed by targeted multiple regression to assess the relationship between hepatic IR or hepatic fat and adipose IR, hepatic gluconeogenesis, VAT, carbohydrate oxidation, androgens, metformin or OPC use and presence of OSA. As an exploratory analysis, the four groups will also be compared using an ANOVA. We recognized that we may not be powered for these analyses, but the data will be used as hypothesis generating for future studies.

The rate of hepatic De Novo lipogenesis is a secondary outcome. Based on our preliminary data that plasma markers of hepatic De Novo lipogenesis are 40% greater in those with fatty liver disease and the use of a high carbohydrate and fructose drink to increase the differences between groups, 10 subjects in each group will be needed to detect a difference in hepatic De Novo lipogenesis^{21,49,52}. The rate of hepatic De Novo lipogenesis will be correlated with measures of hepatic and adipose IR and MRI measures of NAFLD.

Non-Isotope OGTT calculations: The Matsuda model of IR will be used, and B-cell function [insulinogenic index ($\Delta I30/\Delta G30$) and ($\Delta C30/\Delta G30$) and disposition index ($1/IFasting \times \Delta I30/\Delta G30$) and ($1/CFasting \times \Delta C30/\Delta G30$) will be calculated^{40,53-55}.

Proposed Mathematical Model of Glucose and Glycerol Dynamics: The differential equations-based isotope labeled oral glucose minimal model (OMM*)⁵⁶ will be adapted to describe glucose and glycerol dynamics present in the collected data. In OMM*, the oral glucose minimal model (OMM) is modified to account for labeled glucose oral data obtained with the inclusion of a stable isotope tracer. This refinement allows an estimate of insulin sensitivity which is unique in that it accounts for both stimulation of adipose and muscle glucose uptake and inhibition of hepatic glucose release. In OMM*, glucose concentration G and insulin action on glucose disposal X are governed by the following equations:

$$\begin{aligned}\frac{dG}{dt} &= -[S_G^* + X^*] \cdot G + \frac{R_a(\alpha, t)}{V^*} \\ \frac{dX^*}{dt} &= -p_2^* \cdot X^* + p_3^* \cdot [I - I_b]\end{aligned}$$

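### The primary PCOS v control test cannot carry the OSA adjustment promised elsewhere, and the plan does not adjust this non-randomised comparison for race, body fat or time since menarche

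*Combined protocol and SAP*

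**What the plan says.** The Overall Project Statistical Plan defines the endpoint: "The primary outcome is hepatic IR measured as IC₅₀ glucose Ra". It then gives the primary comparison: "Differences between the two primary groups (PCOS, controls) will be assessed with a t test", or with a rank test (Mann-Whitney U is the example) if the data are non-normal. No covariate is named for it. The sample size rests on "a two-tailed t-test and an alpha of 0.05", with "completing 13 controls and 32 PCOS provides 86% power to detect a difference of 35 IU/L in the insulin concentration".

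Four other places bear on the same comparison.

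- **Analysis of the sleep study (section VII).** The closing sentence commits to adjusting all measures for OSA as a yes/no variable, for AHI severity, or for both. The preliminary polysomnogram data earlier in the protocol raise OSA as a possible confounder of the primary outcome.
- **Statistical Plan for Method Development (section VII).** For the oral-glucose v clamp comparison: "Subjects in the two groups will be matched on PCOS diagnosis, race, percent body fat, percent liver fat, and time post-menarche". The outcomes there include the insulin concentration for 50% suppression.
- **Body Composition (III.D.8).** DEXA is justified because "the amount of muscle mass is needed to standardize the OGTT results, since body weight can vary greatly".
- **Secondary analyses (section VII).** A multiple regression of hepatic IR or hepatic fat is planned. Its listed terms include visceral fat, androgens, drug use and OSA, but not race, percent body fat or time since menarche.

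Subjects come from several clinics and the community. Eligibility spans ages 12-21 and BMI from the 90th percentile upward, with a 300-lb limit.

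**The concern.** There are two linked problems. First, the primary analysis is not determined by the plan. One sentence prescribes a t test or Mann-Whitney U. Another prescribes an adjustment that neither test can hold, and it leaves the form of that adjustment open. Two analysts following the document could report different primary results.

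Second, the groups differ by diagnosis and referral route. Any imbalance in adiposity, maturity or race that is related to hepatic insulin resistance would be read as a PCOS effect. The investigators regard these three variables as relevant to the same type of outcome, because they match on them in the method comparison. Nothing in the plan does the equivalent for PCOS v control.

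**Working it through.** **Inputs from the documents.** Difference 35; two-sided alpha 0.05; 13 controls and 32 PCOS (power sentence); 20 controls and 60 PCOS planned to complete (III.B). The SD is 39, from "SD=39 units for glucose IC50" in the equivalence calculation. The power sentence itself states no SD.

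**Assumed inputs (the documents give none).** Covariate-IC50 correlation r = 0.3-0.5; group imbalance g = 0.3-0.6 SD; for the adjusted model, R² = 0-0.4 and variance inflation factor (VIF) = 1.0-1.5.

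**1. The plan's own power figure.** SE = SD × √(1/n₁ + 1/n₂) = 39 × √(1/13 + 1/32) = 12.83. Noncentrality = 35/12.83 = 2.73 on 43 df. Two-sided power is 76% (noncentral t) or 78% (normal), not 86%. A two-sided 86% needs an SD of about 34.2 (t) or 35.0 (normal). A one-sided 0.05 test at SD 39 gives 85-86%. Because the SD actually used is not stated, the 86% cannot be called wrong. SD 39 serves below only as the scale.

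**2. Shift from an unadjusted covariate.** Shift = r × g × SD.
- Low: 0.3 × 0.3 × 39 = 3.5 units, and 3.5/35 = 10% of the target.
- High: 0.5 × 0.6 × 39 = 11.7 units, and 11.7/35 = 33% of the target.

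**3. Rejection rate with no true PCOS effect.** Noncentrality = shift/SE, two-sided 0.05.

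| Groups | SE | Shift 3.5 | Shift 11.7 |
|---|---|---|---|
| 13 v 32 | 12.83 | 3.51/12.83 = 0.27, rate 6% | 11.7/12.83 = 0.91, rate 14% |
| 20 v 60 | 39 × √(1/20 + 1/60) = 10.07 | 3.51/10.07 = 0.35, rate 6% | 11.7/10.07 = 1.16, rate 21% |

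The shift does not shrink with sample size while the SE does, so completing the planned enrolment makes the false-positive rate worse.

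**4. What adjustment does to power.** Residual SD = 39 × √(1 − R²); SE multiplied by √VIF; df = N − 2 − 3, with race counted as one term.

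| Case | 13 v 32 | 20 v 60 |
|---|---|---|
| Unadjusted | 76% | 93% |
| R² 0, VIF 1.5 (least favourable) | 58% | 80% |
| R² 0.2, VIF 1.25 (0.8 × 1.25 = 1, so they cancel) | 76% | 93% |
| R² 0.4, VIF 1.0 (most favourable) | 93% | 99% |

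A weak covariate set can cost power: at 13 v 32 with R² 0.09 and VIF 1.25, power is 70% against 76% unadjusted. A fourth term for OSA changes these powers by 0.1 point or less at the same R² and VIF.

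**5. Race coding.** III.B projects five categories, three of them with 3 or 4 of 105 subjects. Scaled to 20 controls, that is 3/105 × 20 = 0.6 to 4/105 × 20 = 0.8 girls per category. They cannot be fitted as separate terms.

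**The case against.** Several points on the other side are fair.

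- **A reader might infer that the primary comparison is wholly unadjusted by design.** The documents do not support that. Taken literally, the sleep-study text promises an OSA/AHI adjustment that covers the primary outcome. The defect is that the named tests cannot deliver it and no model is given.
- **A reader might infer that the plan contradicts itself by matching in one place and not in another.** It does not. The matching serves oral glucose v clamp, where PCOS diagnosis is itself a matching factor. It shows that the variables are thought relevant, not that the investigators hold they must be balanced between PCOS and controls. The DEXA statement likewise concerns muscle mass for scaling, not percent body fat as a group covariate.
- **Confounding is partly limited.** Both groups are sedentary females aged 12-21 at or above the 90th BMI percentile, without diabetes. The secondary regression includes visceral fat and OSA. This narrows the imbalance but does not remove it, and the secondary regression does not alter the primary test.
- **Body fat may be part of the PCOS phenotype.** The proposed mechanism runs through adipose tissue and visceral fat, so adjusting for total fat changes the question asked. This stands, and is why a model without body fat should also be reported.
- **A reader might argue that adjustment would recover lost power.** That does not hold up. At 20 v 60 the unadjusted test already has 93% power at SD 39, and adjustment can lower power when covariates differ by group.
- **Time since menarche is not listed as a data item.** It is implied by the PCOS criterion and by the matching, but its collection in controls is unconfirmed.

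**Conclusion.** The point holds on bias control and on the unfixed primary model. The prescribed test and the promised OSA/AHI adjustment cannot both be carried out as written, and no section adjusts or matches PCOS v control on race, percent body fat or time since menarche.

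The shift of 3.5-11.7 units (10-33% of the target) and the rejection rates of 6-14% and 6-21% illustrate what could happen. They are not estimates for this cohort: they rest on assumed correlations and imbalances, and on an SD borrowed from the equivalence calculation. The 20 v 60 figures also assume that all 60 planned PCOS girls, treated and untreated, enter the primary PCOS group, which the plan does not say. The direction of any bias is unknown, and it could also mask a true difference. This should be changed, but it does not invalidate the study.

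**What to change.** Prespecify one linear model for IC50 glucose Ra, on the log scale if skewed by a rule set in advance. Include group, DEXA percent body fat, time since menarche and race with sparse categories collapsed. In the same text:

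- state whether OSA/AHI enters this model or a sensitivity analysis, and in which form (yes/no or AHI), so that the group-comparison and sleep-study sentences agree;
- confirm that time since menarche is recorded for every girl, including controls;
- report the unadjusted t test, and the model without body fat, as supportive;
- leave percent liver fat out, because the protocol places it on the proposed pathway.

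The cost is SAP wording, a few degrees of freedom, and possible variance inflation if the covariates correlate with group. Over R² 0-0.4 and VIF up to 1.5, power at 20 v 60 stays at about 80% or above. No new measurement is needed unless time since menarche proves not to be recorded.
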